3.4.1 Definition of Maximum Tolerated Dose

The MTD is defined as the highest dose of AFM24 if both of the following criteria are fulfilled:

- The posterior probability of the true DLT rate being in the target interval ($\geq 16\%$ to $<33\%$) is $>50\%$ with less than 25% risk of the true DLT rate being above 33%; and
- At least 6 subjects have been treated at that cohort in the first cycle of AFM24 treatment under that dosing schedule.

As described in Section 3.4.3, an RP2D can be declared if:

- The MTD criteria are not met on any dose level and/or clinical and laboratory data indicate an optimal biologically active dose has been reached (with less than 25% risk of the true DLT rate being above 33%).

AND

- At least 6 subjects have been treated at that dose level.

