3.4 Dose Escalation Phase (Phase 1)

Phase 1 will employ an adaptive BLRM with 2 parameters guided by the EWOC principle to make dose recommendations and estimate the MTD (Section 9.3.4.1). It is estimated that approximately 25 to 41 subjects will be enrolled into Phase 1 of the study. The number of subjects is dependent on the tested dose cohorts and safety profile of AFM24. As multiple centers will contribute to the enrollment a communication plan will be established to ensure distribution of safety data and study progress amongst the participating centers.

Dose-limiting toxicities (DLTs) will be assessed in the first treatment cycle (ie, the first 4 weeks of treatment for each subject), referred to as the DLT observation period.

The starting dose of AFM24 in the first dose cohort is 14.0 mg administered as an i.v. infusion on a once weekly dosing schedule divided into 4-week cycles.

Dose Cohorts 1 and 2:

To minimize the number of subjects treated at potentially subtherapeutic dose levels in the dose escalation phase (Phase 1), the first 2 dose cohorts will enroll a minimum of 2 subjects. The first 2 subjects of each dose cohort will begin treatment in a staggered approach with at least 7 days between first dosing of these 2 subjects. After the first subject in each cohort has begun treatment and been observed for at least 7 days, additional subjects within the cohort may begin treatment concurrently. All subjects who start treatment need to complete the 28-day DLT observation period or experience a DLT before the SRC meeting and dose escalation decision. A minimum of 2 subjects needs to be evaluable for DLT assessment (Section 3.4.2) to allow for a dose escalation decision by the SRC. If none or only 1 of the subjects is evaluable for DLT assessment, replacement subject(s) will be enrolled. The dose cohorts might be extended to up to 6 subjects based on the SRC decision.

Dose Cohort 3 and any Subsequent Cohorts:

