The objective of the design is to determine the MTD defined as the highest dose with less than 25% risk of the true DLT rate being above 33%. The escalation Phase 1 dose-finding will be guided by a Bayesian 2-parameter logistic regression model with overdose control. These designs have been shown to be superior regarding the precision of MTD determination compared with 3+3 designs.

The model is formulated as follows:

$$\text{logit}(p(d)) = \log(\alpha) + \beta * \log(d/d^*),$$

where $\text{logit}(p) = \log(p/(1-p))$. $p(d)$ represents the probability of having a DLT in the first cycle at dose d , $d^* = 180$ mg is the reference dose, allowing for the interpretation of α as the odds of a DLT at dose d^* , and $\theta = (\log(\alpha), \log(\beta))$ with $\alpha, \beta > 0$ is the parameter vector of the model.

Since a Bayesian approach is applied, a prior distribution $\pi(\theta)$ for the unknown parameter vector θ needs to be specified. This prior distribution will be specified as a multivariate normal distribution, ie,

$$\pi(\theta) = \text{MVN}(\mu, \Sigma)$$

the multivariate normal distribution with mean vector μ and covariance matrix Σ , with

$$\Sigma_i = \begin{pmatrix} \sigma_{i,11}^2 & \sigma_{i,11}\sigma_{i,22}\rho_i \\ \sigma_{i,11}\sigma_{i,22}\rho_i & \sigma_{i,22}^2 \end{pmatrix}$$

Prior derivation

For the current study, data from the non-clinical animal studies were available. Therefore, the observed toxicity data from a study in animals is used to derive the prior.

Prior from nonclinical data:

The starting dose of AFM24 will be 14.0 mg ($200 \mu\text{g}/\text{kg} \times 70 \text{ kg}$ body weight), which is presumed to be at the lower end of the pharmacologically active dose range. No critical toxicities were observed in the cynomolgus toxicity studies up to the maximum applied AFM24 dose level of 75 mg/kg and furthermore, the bispecific NK engagers (in contrast to bispecific T cell engagers) tested so far by Affimed in nonclinical and clinical studies, were all well tolerated up to high dose levels. It is therefore highly unlikely that a severe toxicity defined as DLT in this study would occur at this starting dose, leading to the prior assumption that the median DLT rate at 14 mg is 0.1%. On the other hand, assuming dose-proportionality in humans using a cautious approach, the median DLT rate at the highest planned dose = 1000 mg was therefore assumed 25%.

Table 8: Summary of Prior Distribution

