14.5.1.1 Hypothetical Data Scenarios

Hypothetical data scenarios are shown in [Table 19](#). These scenarios reflect potential on-study data constellations and related escalation as allowed by the model and the 200% escalation limit. For each scenario, the probability of overdose for the current dose, as well as the next potential dose and related probabilities of under-dosing, target dose and over-dosing are shown.

For example, scenario 1 represents the case that no DLT is observed in the first subject at the starting dose of 14 mg. In this case, the next dose permitted by the model and by the 200% escalation rule is 40 mg. In scenario 5a, while no DLT was observed at dose 14 mg, 1 DLT is observed in the first 2 subjects at 40 mg and the model would then not allow to escalate and would require to stay at 40 mg and treat 4 more subjects at 40 mg before escalating to 120mg (scenario 5b). In scenario 9b, an intermediate dose escalation is shown: While no subject experienced a DLT at dose levels 14 mg and 40 mg, 1 DLT was observed at 120 mg. The model would require that in total 6 subjects are treated at 120 mg and would thereafter only allow to escalate to 200 mg (and not to the maximum of the next level, which is 360 mg), to prevent potential overdosing. These cases illustrate the adaptive behavior of the model.

Table 19: Hypothetical Data Scenarios

Scenario	Dose	Data - #DLT	Data - #Sub	CD - P(OD)	Next Dose	ND - P(UD)	ND - P(TD)	ND - P(OD)
1	14	0	2	0.014	40	0.881	0.085	0.035
2	14	1	2	0.322	7	0.500	0.251	0.249
3	14	1	3	0.207	14	0.524	0.269	0.207
4	14	0	2	0.012	120	0.788	0.135	0.076
	40	0	2					
5a	14	0	2	0.209	40	0.506	0.285	0.209
	40	1	2					
5b	14	0	2	0.041	120	0.461	0.306	0.233
	40	1	6					
6	14	1	6	0.052	120	0.486	0.317	0.197
	40	0	3					
7	14	0	2	0.603	7	0.466	0.299	0.235
	40	2	2					

Scenario	Dose	Data - #DLT	Data - #Sub	CD - P(OD)	Next Dose	ND - P(UD)	ND - P(TD)	ND - P(OD)
8	14	0	2	0.013	360	0.571	0.184	0.245
	40	0	2					
	120	0	3					
9a	14	0	2	0.159	120	0.526	0.315	0.159
	40	0	2					
	120	1	3					
9b	14	0	2	0.043	200	0.471	0.312	0.217
	40	0	2					
	120	1	6					
10	14	0	2	0.221	120	0.344	0.434	0.221
	40	0	2					
	120	2	6					
11	14	0	2	0.062	360	0.487	0.293	0.220
	40	0	2					
	120	1	6					
	200	0	3					
12	14	0	2	0.036	1000	0.585	0.190	0.225
	40	0	2					
	120	0	3					
	360	0	3					
13	14	0	2	0.280	200	0.685	0.251	0.063
	40	0	2					
	120	0	3					
	360	1	3					

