14.5.1.2 Operating Characteristics

Operating characteristics are a way to assess the long-run behavior of a model. Under an assumed true dose-toxicity curve, metrics such as the probability of recommending a dose with true DLT rate in the target interval can be approximated via simulation Table 20 describes 3 assumed true dose-toxicity scenarios which were used to assess the operating characteristics of the model. These scenarios reflect a wide range of possible cases as follows:

Scenario 1 (P): aligned with prior means

Scenario 2 (H): high-toxicity scenario

Scenario 3 (LH): low-toxicity followed by high-toxicity

Table 20: Assumed True Dose-Toxicity Scenarios

Scenario								
		7 mg	14 mg	40 mg	120 mg	200 mg	360 mg	1000 mg
1 (P)	P (DLT)	0.061	0.075	0.108	0.178	0.244	0.342	0.486
2 (H)		0.150	0.200	0.250	0.350	0.400	0.450	0.500
3 (LH)		0.005	0.070	0.100	0.300	0.350	0.450	0.500

DLT = dose-limiting toxicity; H = high toxicity; LH = low-high toxicity; P = assumed true-dose toxicity.

Bold numbers indicate true DLT rates in the target interval [0.16-0.33].

For each of these scenarios, 500 studies were simulated. It was then assessed how often a dose was declared as MTD with true DLT rate in the under-, targeted or over-dose range. Furthermore, the average, minimum, and maximum number of subjects per study and the average number of DLTs per study are reported. Results are shown in [Table 21](#).

Table 21: Hypothetical Data Scenarios

Scenario	% of studies declaring an MTD with true DLT rate in				# Subjects	# DLT
	Underdose	Target dose	Overdose	Stopped		
1 (P)	29.0	51.2	18.0	1.8	18.57 (1-43)	3.26 (1-11)
2 (H)	1.4	58.6	17.4	22.6	13.90 (1-38)	3.55 (1-12)
3 (LH)	47.2	33.8	17.0	2.0	17.65 (1-42)	3.45 (1-10)

DLT = dose-limiting toxicity; H = high toxicity; LH = low toxicity; Max = maximum; Min = minimum;

MTD = maximum tolerated dose; P = assumed true dose toxicity.

In Scenario 1, which reflects the case that the true dose-toxicity is aligned with prior means, 51.2% of the simulated studies declared a dose as MTD with true DLT rate in the targeted dose range. Since the dose of 1000 mg has a DLT probability of 48.6% it was identified quite rarely as MTD, namely in 4 case of the simulated cases.

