In Scenario 2 (high-toxicity scenario), the starting dose has already 20% probability of observing at least 1 DLTs in the first cohort if 2 subjects enrolled. This contributes to the high percentage 22.6% of all simulated studies for which the study is stopped since none of the doses is considered tolerable anymore. This is an expected situation for a high-toxicity scenario.

In Scenario 3, 33.8% of the simulated studies declared a dose as MTD with true DLT rate in the targeted dose range.

The mean subject numbers range from 13.9 subjects (high scenario) to 18.57 subjects (true dose toxicity scenario) and the maximum number of subjects was 43. The low mean number of subjects in the high toxicity- scenario is explained by the frequent stopping of the study.

In summary, the considered data scenarios show a reasonable behavior of the model and the operating characteristics demonstrate a good precision of MTD determination.

14.6 APPENDIX F: Grading and Management of Infusion-related Reactions, including Anaphylaxis, Allergic Reaction, and Cytokine Release Syndrome

Investigators are asked to pay special attention to IRRs, which include hypersensitivity reactions and CRS. These reactions may be experienced by subjects during the infusion of investigational treatment (uniphasic reaction) and/or within hours of an infusion (biphasic/delayed reaction). The reaction may be caused by the therapeutic agent, diluent, or delivery vehicle. IRRs can have a broad variety of symptoms; from mild to moderate chills, flushing, itching, skin rashes, heart rate/blood pressure alterations, dyspnea, chest discomfort, back/abdominal pain, nausea, vomiting, diarrhea to severe and life threatening anaphylactic/anaphylactoid reactions; mostly appearing during or immediately after the investigational drug infusion. Special attention must be paid to CRS during investigational treatment which can manifest with fever, cardiac dysfunction, acute respiratory distress syndrome, neurologic toxicity, renal and/or hepatic failure, and disseminated intravascular coagulation. Skin rash, as well as gastrointestinal symptoms of nausea, vomiting or diarrhea may also occur. Fever is a hallmark for CRS, and many features of CRS can also mimic infection.

The aim of this appendix is to:

Provide guidance on monitoring for IRR/CRS

Provide guidance on the grading of IRR/CRS

Provide guidance on management of IRR/CRS.

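### Protocol sections 3.4.1 and 9.3.4.1 give two different MTD rules that can disagree on the same data, and the Table 21 operating characteristics do not come from the full 3.4.1 rule

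*Protocol*

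**What the plan says.** **Protocol 3.4.1** makes the MTD the highest dose that meets all of the following: "The posterior probability of the true DLT rate being in the target interval" (16% to below 33%) is above 50%; the risk of a true DLT rate above 33% is below 25%; and at least 6 subjects have been treated there. It also foresees that no dose qualifies, in which case an RP2D can be declared: "The MTD criteria are not met on any dose level and/or clinical and laboratory data indicate an optimal biologically active dose has been reached", with a 25% overdose limit in brackets and again at least 6 subjects.

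**Protocol 9.3.4.1** gives the design objective as determining "the MTD defined as the highest dose with less than 25% risk of the true DLT rate being above 33" per cent. It has no target-interval condition and no minimum number.

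**Cross-references.** The note under Figure 3 in 9.3.4.1 sends the reader to 3.4.3 for the definition. Section 3.4.1 also refers to 3.4.3, and 3.4.3 cites itself. SAP 7.7.1 refers back to the Protocol.

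**Protocol 14.5.1.2.** Table 21 reports the percentage "of studies declaring an MTD with true DLT rate in" the under-, target and overdose ranges, plus the percentage stopped. For scenario 1 the text says that "51.2% of the simulated studies declared a dose as MTD with true DLT rate in the targeted dose range", and it concludes that "the operating characteristics demonstrate a good precision of MTD determination". The declaration rule used in the simulation is not given.

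**Cohort size.** Section 3.4 states: "The dose cohorts might be extended to up to 6 subjects based on the SRC decision". Section 3.6 likewise limits expansion to 6 evaluable subjects, while 3.4.3 allows expansion below an unacceptable dose without giving a number.

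**The concern.** Determining the MTD is part of the Phase 1 primary objective, and the study report must say whether an MTD was reached. With two rules in force, the same data can support either statement. Table 21 is the plan's evidence that dose finding works. If 3.4.1 is the governing rule, that evidence describes a procedure other than the one to be applied, and the reader cannot tell how often 3.4.1 would end without an MTD.

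**Working it through.** **Inputs.** Model, with reference dose 180 mg: logit p(d) = log α + β·log(d/180). Prior (Table 8): log α ~ N(−1.983, 2.000²), log β ~ N(−0.217, 1.000²), correlation 0. The posterior was computed on a grid. True DLT rates are from Table 20, with P, H and LH denoting its scenarios 1, 2 and 3.

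**Step 1: reproduce Table 19.**

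| Data | Quantity | Table 19 | Grid |
|---|---|---|---|
| Scenario 10: 0/2 at 14, 0/2 at 40, 2/6 at 120 mg | P(under) / P(target) / P(over) at 120 mg | 0.344 / 0.434 / 0.221 | 0.344 / 0.433 / 0.224 |
| Scenario 13: 1/3 at 360 mg | P(over) at 360 mg | 0.280 | 0.280 |
| Scenario 2: 1/2 at 14 mg | P(over) at 7 mg | 0.249 | 0.253 |

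The last row matters because 7 mg sits on the 25% boundary. The simulations below therefore use an admissibility cut of 0.255, so that 7 mg stays open as in Table 19.

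**Step 2: apply both rules to the same data.**

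- *Scenario 10, at 120 mg.* P(over) = 0.221 < 0.25, and Table 19 gives 120 mg as the next permitted dose, so 120 mg is the MTD under 9.3.4.1. P(target) = 0.434 < 0.50, so under 3.4.1 it is not.
- *Clean six-subject top dose.* For 0/6 at 480 mg with no DLT assumed at lower doses, P(over) is about 0.002 and P(target) about 0.03. Using the 480 mg data alone, they are 0.021 and 0.117. If candidates are limited to doses tested, 9.3.4.1 calls this the MTD; 3.4.1 does not.
- *Six subjects at 120 mg after clean lower doses.* P(target) is 0.045, 0.246, 0.433 and 0.382 for 0, 1, 2 and 3 DLTs, so none reaches 0.50. With clean lower doses, 3.4.1 is first met at 120 mg with 3/10 (P(target) 0.517, P(over) 0.203); at 360 mg it is met with 3/11 (0.522, 0.215). It can be met with six per dose when DLTs occur at two levels: 2/6 at 120 mg and 2/6 at 200 mg give P(target) 0.552 at 120 mg.

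**Step 3: add the Table 21 rows (under + target + over + stopped).**

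- P: 29.0 + 51.2 + 18.0 + 1.8 = 100.0
- H: 1.4 + 58.6 + 17.4 + 22.6 = 100.0
- LH: 47.2 + 33.8 + 17.0 + 2.0 = 100.0

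Every simulated study either stopped or declared an MTD. The outcome that 3.4.1 itself foresees, no dose qualifying, never occurs.

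**Step 4: simulate the full 3.4.1 rule.** Start at 14 mg; cohorts of 2, 2, then 3; next dose admissible and at most 3 times the current dose; at most 43 subjects; 1,000 studies per scenario.

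| | Under | Target | Over | Stopped | No MTD | Mean N |
|---|---|---|---|---|---|---|
| P, Table 21 | 29.0 | 51.2 | 18.0 | 1.8 | none shown | 18.57 |
| P, 3.4.1 | 15.8 | 52.5 | 19.0 | 2.1 | 10.6 | 25.0 |
| H, Table 21 | 1.4 | 58.6 | 17.4 | 22.6 | none shown | 13.90 |
| H, 3.4.1 | 1.5 | 52.8 | 19.9 | 24.0 | 1.8 | 16.7 |
| LH, Table 21 | 47.2 | 33.8 | 17.0 | 2.0 | none shown | 17.65 |
| LH, 3.4.1 | 24.6 | 33.1 | 21.2 | 0.7 | 20.4 | 26.2 |

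A separate rerun gave in-target 52.0/54.0/35.5%, no MTD 10.2/1.2/19.7% and mean N 24.7/17.4/25.9. The underdose share falls by about half: 15.8/29.0 = 0.54 in P and 24.6/47.2 = 0.52 in LH.

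**Step 5: the same rule with a strict six per dose.** No MTD in 74.2/63.4/81.7% of studies.

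**Step 6: the 9.3.4.1 rule, with six subjects required at the declared dose (an added assumption).** Under/target/over/stopped is 26.6/50.8/19.0/3.6 (P), 0.8/56.2/22.8/20.2 (H) and 45.2/33.5/20.4/0.9 (LH), with no undeclared studies. The shares are close to Table 21 (largest gap 22.8 − 17.4 = 5.4 points), but mean N is 15.6/12.7/15.0, which is too low.

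**The case against.** **The selection claim survives.** Without a per-dose cap, in-target selection under 3.4.1 is about what Table 21 reports. That stands. A reader might infer from the six-per-dose results that the true correct-selection rate is a small fraction of 51.2%. The documents do not support this: 3.4.1 says at least 6, 3.4.3 permits expansion without a number, and Table 21's largest study has 43 subjects, more than the 7 × 6 = 42 that a strict cap over the seven doses of Table 20 allows.

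**The source of Table 21 is unknown.** A reader might infer that 9.3.4.1 produced it. That is not established. Mean N does not match, and Table 21's minimum of 1 subject is inconsistent with starting cohorts of two. With the cut at exactly 0.25 the stopped shares become 15.4/41.6/13.0%. A hybrid rule (six at the dose, plus either the 50% condition or at least 15 subjects in total) fits about as well. Only the negative statement is firm.

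**Table 19 illustrates escalation, not declaration.** Its description reads: "For each scenario, the probability of overdose for the current dose, as well as the next potential dose and related probabilities". That is fair, so low target probabilities elsewhere in the table carry little weight. Scenario 10 still counts, because there the next dose is the current one, with six treated.

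**The RP2D bracket.** A reader might infer that an RP2D reached by the no-MTD route has no overdose limit. The bracket most naturally covers both routes, and overdose control bars an inadmissible dose from the next cohort. For example, 2/6 at 360 mg after clean lower doses has overdose risk 0.32, so the wording could be clearer, but this is a minor point.

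**Reporting.** SAP 7.7.1 already reports the predicted overdose probability for every dose level, so no further request is needed.

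**Conclusion.** The concern holds in this form. The two MTD definitions conflict, nothing in the protocol or SAP says which governs, and they give opposite answers on Table 19 scenario 10 and on a clean six-subject top dose. Table 21 does not represent the full 3.4.1 rule.

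Without a per-dose cap, adopting 3.4.1 leaves correct selection roughly where it is. It adds a no-MTD outcome in about 10/1/20% of studies, about halves the underdose share in P and LH, and raises mean N to about 25/17/26. With a strict cap of six, 63–82% of studies declare no MTD. These sizes rest on the Step 4 design assumptions and on the 0.255 cut; simulation error is about ±4 points for Table 21's 500 studies.

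A reader might infer that the 480 mg dose is in doubt. It is not. Section 1.6 reports no DLT in 6 subjects there, and the overdose risk is 0.002–0.021 with no DLT assumed below, or 0.058 if 2 of 23 lower-dose subjects had one (assumed; the intermediate doses and counts below 480 mg are also assumptions). What remains open is how the Phase 1 MTD conclusion is worded in the study report, including for the 720 mg cohort. The sponsor should settle this before reporting.

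**What to change.** 1. Use one MTD definition in 3.4.1 and 9.3.4.1, and make 9.3.4.1 and 3.4.3 refer to 3.4.1.
2. If the 50% target condition is kept, rerun Table 21 under it, add a column for studies declaring no MTD, and state the declaration rule and the per-dose maximum.
3. If the 25% rule plus at least 6 subjects is adopted instead, state that a top dose with low target probability and no higher dose excluded by the model is reported as MTD not reached.
4. Optional: state in 3.4.1 that the 25% limit applies to an RP2D by either route.

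The cost is wording in 3.4.1, 3.4.3 and 9.3.4.1 and, under option 2 only, a rerun of three scenarios of 500 studies. No subjects are added, and the posterior is already computed at each model update.

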3.4.2 Definition of Dose-Limiting Toxicity (DLT)

Dose-limiting toxicity is defined as an AE or abnormal laboratory value assessed as unrelated to underlying disease, disease progression, inter-current illness, or concomitant medications, that occurs ≤ 28 days following the first dose of AFM24 (Cycle 1) and that meets any of the following criteria shown in Table 3. Clinically relevant toxicities will be evaluated according to the National Cancer Institute (NCI)/National Institutes of Health CTCAE v5.0. Subjects who experience a DLT during Cycle 1 must permanently discontinue AFM24.

Subjects must receive $\geq 80\%$ of their assigned AFM24 dose in Cycle 1 and complete the 28-day DLT observation period or have had a DLT within the first cycle of treatment to be considered evaluable for DLT.

For dose-escalation decisions, only DLTs occurring during Cycle 1 of treatment will be considered in the 2-parameter BLRM.

Table 3: Definition of Dose Limiting Toxicity

Toxicity	Any of the following criteria
Hematological ^a	\geq CTCAE Grade 4 neutropenia (ANC $<0.5 \times 10^9/L$) lasting for longer than 4 consecutive days
	Febrile neutropenia (ANC $<1.0 \times 10^9/L$ of any duration accompanied by fever $\geq 38.5^\circ C$ or systemic infection)
	CTCAE Grade 3 thrombocytopenia (platelets 25 to $<50 \times 10^9/L$) associated with bleeding
	CTCAE Grade 4 thrombocytopenia (platelets $<25 \times 10^9/L$)
	\geq CTCAE Grade 4 anemia that is considered to be treatment related
Non-hematological	
Any \geqCTCAE Grade 3 AE including, but not limited to:
 
• CTCAE Grade 3 infusion-related reaction/cytokine release syndrome not responsive to symptomatic treatment within 6 hours (ie, no improvement to Grade 2 or better within 6 hours with optimal medical management)• CTCAE Grade 4 infusion-related reaction/cytokine release syndrome• QTcF prolongation (>500 msec)

Toxicity	Any of the following criteria
	
 CTCAE Grade 3 hypertension for >14 consecutive days despite optimal anti-hypertension therapy CTCAE Grade 4 hypertension ≥CTCAE Grade 3 total bilirubin (>3×ULN) ≥CTCAE Grade 3 ALT, AST, or ALP (>5×ULN) Subjects without hepatic metastasis: subjects fulfilling Hy's law criteria or 1.5 times increase from baseline value of total bilirubin for >2 weeks^b; Subjects with hepatic metastasis: 1.5 times increase from baseline value of total bilirubin for >2 weeks^b; ≥CTCAE Grade 3 vomiting or nausea for ≥72 hours despite optimal anti-emetic therapy; and/or ≥CTCAE Grade 3 diarrhea for ≥72 hours despite optimal anti-diarrhea treatment
	Any other ≥CTCAE Grade 3 AE not listed above, except for the exclusions noted below
	Inability to receive at least 3 of the scheduled doses of AFM24 in Cycle 1 due to treatment-related toxicity
	
Any other toxicity (irrespective of grade) that:
 
 Is greater than that at baseline and clinically significant and/or unacceptable and/or does not respond to supportive care and judged to be a DLT by the SRC; or Results in a disruption of AFM24 dosing for more than 2 weeks
Exceptions to DLT criteria ^c	Isolated laboratory changes of any grade without clinical sequelae or clinical significance with the exception of those laboratory changes outlined above
	CTCAE Grade 3 fever (in the absence of neutropenia) or fatigue that resolves to <Grade 3 within 72 hours
	CTCAE Grade 3 hypertension for ≤14 consecutive days
	CTCAE Grade 3 nausea, vomiting, diarrhea, or dehydration that resolves to <Grade 3 within 72 hours of initiating optimal supportive care treatment
	CTCAE Grade 3 infusion-related reaction/cytokine release syndrome responsive to symptomatic treatment within 6 hours (ie, improvement to Grade 2 or better within 6 hours with optimal medical management)

AE = adverse event; ALT = alanine aminotransferase; ALP = alkaline phosphatase; ANC = absolute neutrophil count; AST = aspartate aminotransferase; CTCAE = Common Terminology Criteria for Adverse Events; DLT = dose-limiting toxicity; NCI = National Cancer Institute; QTcF = corrected QT interval by Fridericia; SRC = Safety Review Committee; ULN = upper limit of normal.

- Subjects may receive supportive care (eg, use of granulocyte-colony stimulating factor, packed red blood cells, and platelets) as per local institutional guidelines. However, during the DLT observation period, it is not allowed to administer these supportive measures without clinical indication.
- Subjects fulfilling potential Hy's law criteria need to have a repeat blood draw immediately and study drug withheld while the case is reviewed and follow-up assessments are performed. The Investigator will review all previous laboratory data to determine whether potential Hy's Law criteria were met at any study visit prior to or after starting study drug and will review the case with the Medical Monitor and agree on the approach for the subjects' follow-up assessments.
Investigators should use their best judgment based on clinical and radiological criteria to exclude progressive disease as the cause of increased hepatic dysfunction.
- The SRC will closely monitor and review all AEs including the incidences of the AEs listed under the "Exceptions to DLT criteria" during the scheduled and any ad-hoc SRC meetings.

Note: NCI CTCAE v5.0 will be used for all grading.

